11.3 Sample Size Determination

Sample size for Heart Matters was calculated on the basis of observing a 1.8 kg difference (SD = 3.2) in the primary outcome – weight change – between two intervention groups from baseline to 6 months. We determined a sample of 102 would allow us to detect a 1.8 kg difference (SD = 3.2) in weight change between intervention and control groups, with 80% power and an α of 0.05. Accounting for attrition and intra-class correlation, due to a clustered randomized delayed intervention design, we plan to enroll 120 participants.

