3 SYNOPSIS

Trial Title	Cardiovascular Outcomes of an Adapted Evidence-Based Intervention for Rural African Americans: Heart Matters Trial		
Internal ref. no. (or short title)	Heart Matters		
Trial registration	NCT02707432 Date of registration: March 14, 2016 https://clinicaltrials.gov/ct2/show/NCT02707432?term=[name]&draw=2&rank=2		
Funder	National Heart, Lung, and Blood Institute (NHLBI; 5R01HL120690)		
Trial Design	Randomized, controlled trial		
Trial Participants	African American adults (21 years or older) with at least one risk factor for cardiovascular disease.		
Sample Size	140		
Planned Trial Period	Total length of the project is 18 months. Participant's involvement will be a 12-month intervention with a 6-month follow-up.		
Planned Recruitment period	March 27, 2017 – February 28, 2019		
	Objectives	Outcome Measures	Timepoint(s)
Primary	To determine the effect of an adapted intervention, Heart Matters, on cardiovascular clinical outcomes.	Body weight	6 months
Secondary	To determine the effect of Heart Matters on secondary cardiovascular clinical	Systolic and diastolic blood pressures	6 months

	outcome		
Intervention(s)	Lifestyle modification consisting of interactive group and individual visit sessions targeting physical activity, weight loss, and nutrition.		
Comparator	No comparator intervention due to delayed control design.		

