Given the burden of co-morbidities in rural African American populations, interventions targeting only one behavior or risk factor are likely to be less successful than those using intervention components and concepts impacting multiple behaviors. There is a need for culturally adapted interventions that address multiple behavioral risk factors for CVD. Using a Community-Based Participatory Research (CBPR) approach, our team adapted and will implement an EBI to improve cardiovascular risk in African Americans living in a rural underserved setting.

Participants: African Americans who reside in Edgecombe and Nash counties, aged 21 years or older, with at least one self-reported cardiovascular disease (CVD) risk factor.

Potential benefits for study participants include participation in long-term lifestyle modifications that may result in improved diet, nutrition, and physical activity patterns, which in turn should decrease blood pressure and lead to an overall reduction in cardiovascular and cancer morbidity.

Heart Matters Intervention: Heart Matters will use a lifestyle modification to reduce CVD risk factors and includes 26 interactive group sessions and 7 individual visit sessions over 12 months. Heart Matters lifestyle goals include: 1) reducing weight by 15 lbs. or another agreed upon goal, 2) limiting fat intake by consuming 20–50% or less of total calories from fat, 3) limiting daily sodium intake to 2300 mg or less, 4) accumulating 150 min of moderate-intensity exercise each week, 5) limiting alcohol intake; women are advised to consume no more than one alcoholic drink per day and men are advised to consume no more than two alcoholic drinks per day, and 6) diet and physical activity tracking.

Trained facilitators and co-facilitators will conduct 26 90-minute group sessions at each organizational site with 15–20 participants per group. Facilitators are members of the community who are teachers, coaches, or clergy members and have 30 min of group supervision of adherence to protocol for each session delivered. Co-facilitators are allied health professionals, such as nutritionists, nurses, and personal trainers who help deliver the educational content. All facilitators will participate in an extensive three-part training on intervention protocols and curriculum.

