7 TRIAL DESIGN

Heart Matters is a community-based randomized trial comparing the effects of implementing the adapted lifestyle modification intervention on cardiovascular clinical outcomes among African American participants in rural eastern NC.

To implement Heart Matters, we will cluster individual participants within organizations that we recruit to participate in the study and be host sites for the intervention delivery. We will randomize organizations to 2 start times: Time 1 Heart Matters Intervention Group (immediately after baseline data collection) and Time 2 6 month-delay Heart Matters Intervention Group (6 months after baseline data collection). Randomization by organization will reduce the likelihood of data contamination given the fact that rural communities tend to be smaller and participants may be familiar with each other.

The flow of the participant is: 1. Screening at community organization and pre-intervention data collection. 2. Randomization of organizations to treatment group or 6 month delayed intervention control, 3. 6 month assessment data collection.

Data collection procedures: After the consent process, eligible individuals will complete the baseline data collection in a community setting. All data collection will be completed by trained research staff from the partner community organizations, James McFarlin Community Development, Inc and Project Momentum, Inc. Data collection will include biometric and biomarker data as well as self-report behavioral data. Trained research staff will collect biometrics such as weight, height, grip strength, and balance. Trained research staff who are registered nurses will collect blood pressure and hemoglobin A1c. Study staff will record the biometric data on paper forms which will be entered into REDCap, a secure web-based application for data management. For participants with life-threatening A1c levels, they will be immediately transported to emergency services, and adverse event data will be documented by research staff. The baseline questionnaire will include behavioral measures and structured questions on demographics (e.g. age, race, marital status, SES), health history, medications, CVD risk factors. Data collectors will enter data from the paper questionnaire forms into REDCap.

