9 TRIAL PROCEDURES

9.1 Recruitment

9.1.1 Organizational Recruitment

We will recruit organizations to serve as recruitment and intervention sites from both counties (Edgecombe and Nash). We will invite potential organizations based on: (a) existing relationships through the Project GRACE consortium, (b) and a list of organizations beyond existing networks generated by our James McFarlin Community Development, Inc and Project Momentum, Inc collaborators. Knowing that CVD risk is high in older adult populations, the extended list will include senior health and civic organizations. Historically, faith based organizations reach a large segment of the minority community and are a trusted leader in the community. As a result, many organizations may be faith-based.

In addition to partnering for participant recruitment, organizations will be host sites for intervention delivery. We will use the following inclusion criteria to evaluate each organization: kitchen space with refrigerator, stove and/or microwave, contact person from each organization available to open and close the building, and layout of how the used space should look at the conclusion of use. We will base final inclusion criteria on if the site could host the intervention for all 12 months. Of the original list of criteria, we will identify sufficient sites to meet sample size needed.

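### The synopsis plans 140 participants and section 11.3 plans 120, and the stated 80% power is that of 102 independent participants, with no inputs shown for the attrition and clustering allowance

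*Combined protocol and SAP*

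**What the plan says.** The synopsis (section 3) reads "Sample Size 140". Section 11.3 sets out the calculation: "We determined a sample of 102 would allow us to detect a 1.8 kg difference (SD = 3.2) in weight change", at 80% power and α 0.05. It then moves to the enrolment figure: "Accounting for attrition and intra-class correlation, due to a clustered randomized delayed intervention design, we plan to enroll 120 participants".

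On the design, section 7 says "we will cluster individual participants within organizations that we recruit to participate in the study", and it is the organizations that are randomized to the two start times. Section 9.4 pairs organizations by number of participants and assigns one of each pair to each arm.

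The only figure that bears on cluster size is in section 5, which describes "group sessions at each organizational site with 15–20 participants per group". It is not linked to the sample size. Section 9.1.1 gives no number of organizations and says only that "we will identify sufficient sites to meet sample size needed". Section 11.1 confirms that no separate SAP exists, so no other document can settle these points.

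**The concern.** There are two problems. The first needs no assumption: two current sections give different planned totals, and neither is called a minimum, a maximum or an evaluable number. Site recruitment under section 9.1.1 is tied to the required sample size, so it depends on a figure that the protocol gives twice.

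The second is that the stated power is attached to 102, before any allowance. No power is given for either enrolment figure under randomization of organizations. The allowance is attributed to attrition and intra-class correlation together, without a value for either, so a reader cannot tell what weight difference the trial can detect. Power and its reporting are at stake. The effect estimate is not biased by this.

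**Working it through.** **Inputs from the documents.** Difference 1.8 kg, SD 3.2, power 80%, α 0.05, N = 102 rising to 120 (section 11.3); N = 140 (synopsis); organizations randomized (section 7); 15–20 per session group (section 5).

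**Inputs that are assumptions.** Attrition a, ICC, and enrolled participants per organization m. The documents give none of them. For m, I use 15–20 on the premise that one organization supplies one session group, and 5–8 for smaller organizations. Equal cluster sizes are assumed throughout.

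**Step 1. Reproduce 102.** Standardized difference = 1.8/3.2 = 0.5625. A two-sided two-sample t-test at 80% power needs 50.6 per arm, so 51 per arm and 102 in total, with power 80.3%. This matches exactly. A one-sided test gives 80 in total and does not match. The figure of 102 is therefore correct for independent, individually randomized participants.

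**Step 2. Size of the allowance.** 120/102 = 1.176. Attrition that would use all of it: 1 − 102/120 = 15.0%, or 120 × 0.85 = 102. Lower attrition leaves some room: 5% needs 108 and 10% needs 114.

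**Step 3. ICC that 120 can absorb while keeping the power of 102.** With design effect 1 + (m(1−a) − 1) × ICC, the limit is

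ICC = (120(1−a)/102 − 1) / (m(1−a) − 1).

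| Attrition | m = 20 | m = 15 | m = 8 | m = 5 |
|---|---|---|---|---|
| 0% | 0.1765/19 = 0.009 | 0.1765/14 = 0.013 | 0.1765/7 = 0.025 | 0.1765/4 = 0.044 |
| 10% | 0.0588/17 = 0.0035 | 0.0588/12.5 = 0.005 | 0.0588/6.2 = 0.0095 | 0.0588/3.5 = 0.017 |
| 15% | 0 | 0 | 0 | 0 |

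**Step 4. Power for 1.8 kg at each stated size.** Take a = 10% and ICC = 0.01. SE = 3.2 × √(4 × DE / (N(1−a))), and power comes from the noncentral t distribution with noncentrality 1.8/SE. Two choices of degrees of freedom (df) are shown: retained participants minus 2, and organizations (N/m) minus 2.

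Worked case, N = 120 and m = 20: 108 are retained, 18 per organization. DE = 1 + 17 × 0.01 = 1.17. SE = 3.2 × √(4 × 1.17/108) = 0.666. Noncentrality = 2.70. With 106 df (critical value 1.98), power is 76.4%. With 6 − 2 = 4 df (critical value 2.78), it is about 54%.

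| | m = 20 | m = 15 | m = 8 | m = 5 |
|---|---|---|---|---|
| 120, participant df | 76.4% | 78.0% | 80.2% | 81.2% |
| 140, participant df | 82.5% | 84.0% | 86.0% | 86.8% |
| 120, organizations − 2 | about 54% | about 64% | about 75% | about 78% |
| 140, organizations − 2 | about 65% | about 73% | about 82% | about 85% |

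The number of organizations is the plain ratio N/m: 6, 8, 15 and 24 at 120, and 7, 9.3, 17.5 and 28 at 140.

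**Step 5. A higher ICC.** At ICC 0.02 with 10% attrition and participant df, power at m = 20–15 is 71–74% for 120 and 77–80% for 140. At m = 8–5 it is 78–80% and 84–86%.

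**The case against.** The strongest reply is that section 11.3 says in terms that both attrition and intra-class correlation were taken into account, and that every attrition rate, ICC and cluster size used above is mine. That stands, and it limits what can be claimed. Four stronger readings are tempting, and the documents do not support them.

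- **Clustering was ignored.** A reader might infer this because 15% attrition uses the allowance exactly. But the 15% is back-solved from 102/120 and is not in the plan. With less attrition, some allowance for clustering remains.
- **120 is underpowered and 140 is adequate.** The two sizes fall on opposite sides of 80% in some scenarios only. At ICC 0.02 and 15–20 per organization, neither exceeds 80% with participant df. At ICC 0.01 and 5–8 per organization, both reach it. At ICC 0.01 and 15–20 per organization, both fall short with df based on organizations. Section 11.2 does not specify the df method, so the documents establish neither version.
- **140 comes from a different set of assumptions.** Inflating 102 for 15% attrition and ICC 0.01 at 15–20 per organization gives 134–139 using retained cluster size, or 137–143 using enrolled cluster size. That some inputs land near 140 is not evidence of how it arose. It could equally be a recruitment target, an older figure or a slip.
- **102 is wrong.** It reproduces exactly for the calculation it represents.

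It is also fair to say that missing inputs are a reporting gap rather than a demonstrated error. The conflict between 140 and 120, however, is an inconsistency on the face of the protocol.

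**Conclusion.** The point holds in two parts. First, the protocol states two planned sample sizes, 140 and 120, without reconciling them; this rests on no assumption. Second, the 80% power is shown only for 102 independent participants, while organizations are randomized. The factor of 1.176 that is meant to cover attrition and clustering is small and cannot be checked: with no attrition it absorbs an ICC of only 0.009–0.013 at 20–15 per organization, and 0.025 or 0.044 at 8 or 5.

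The choice of size changes power by about 5 to 11 percentage points in the scenarios of step 4. Whether either size reaches 80% depends on attrition, ICC, cluster size and df, and the plan leaves all four open. The power figures assume equal clusters; unequal organizations would generally lower them.

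**What to change.** State one planned sample size in both the synopsis and section 11.3. In section 11.3, show the assumed attrition, the ICC for 6-month weight change, the average number of participants per organization with its expected variation, and the number of organizations. Then restate, for that one size and the cluster-randomized design, either the power for 1.8 kg or the difference detectable at 80% power. Name the method, and use degrees of freedom that reflect the number of organizations. A simple design-effect multiplier is not enough on its own, because it leaves out both the small number of organizations and any imbalance in their sizes.

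This changes text in two places. It asks for no extra enrolment and no change of design. The cost is that the stated power may become less favourable.

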11.4 Analysis Populations

We will implement Heart Matters in Edgecombe and Nash counties; two counties in eastern North Carolina that are considered rural by urbanized area definitions with respective populations of 54,150 and 93,919. The two counties share one urbanized area, the city of Rocky Mount. Both have had a large prevalence of African Americans (56.7 and 40% of population, respectively) that experience significant health disparities with respect to cardiovascular disease. The sample is recruited through community organizations and

thus not considered a randomly selected sample representative of populations.

11.5 The Level of Statistical Significance

A p-value smaller than 0.05 will be considered statistically significant.

11.6 Procedure for Accounting for Missing, Unused, and Spurious Data

For all measures, scores will be calculated if an individual answered at least 60% of the items of a given measure. If an individual answered less than 60% of items, the data will be treated as missing for that measure only.

11.7 Procedures for Reporting any Deviation(s) from the Original Statistical Plan

Any deviations from the original statistical analysis plan will be reported in publications.

12 DATA MANAGEMENT

Data collection will include biometric and biomarker data as well as self-report behavioral data. Hard copy files of data will be retained in locked containers in locked rooms where approved study staff will have access. Data will be entered in REDCap, a secure web-based application for data management. All export of data from REDCap will adhere to university protocols to ensure data is safely stored on university approved servers.

12.1 Access to Data

Direct access will be granted to authorized representatives from the Sponsor, host institution and the regulatory authorities to permit trial-related monitoring, audits and inspections.

12.2 Data Recording and Record Keeping

Trained research staff will collect weight and other data collection except trained research staff who are registered nurses will collect blood pressure and hemoglobin A1c. Study staff will record the biometric data on paper forms, which will be entered into REDCap, a secure web-based application for data management. REDCap provides timestamped tracking to allow for an audit trail of all revisions to database codebook and data itself. Any quality assurance reviews and corrections to data entry will be tracked through REDCap.

Hard copy files will be stored at UNC. The participants will be identified by a unique trial specific number and/or code in any database. The name and any other identifying detail will NOT be included in any trial data electronic file. Informed consent documents and a document linking file that links participant ID to their name will be stored separately from all data.

13 QUALITY ASSURANCE PROCEDURES

13.1 Monitoring

Weekly meetings will be conducted with the team members during all stages of the study to review progress to date, any protocol deviations, data management, safety monitoring, and compliance.

13.2 Scientific Advisory Board

The Scientific Advisory Board will be comprised of PI, Co-Investigator, Project Manager, Biostatistician from the study two and 2 outside experts. The study team will provide a report to the scientific advisory board annually, and the board will discuss and make recommendations to support completion of scientific aims. As this will be a minimal risk study, this oversight is sufficient.

14 PROTOCOL DEVIATIONS

A trial related deviation is a departure from the ethically approved trial protocol or other trial document or process (e.g. consent process) or any applicable regulatory requirements. Any deviations from the protocol will be documented in a protocol deviation form and filed in the trial master file. The protocol deviations and completed forms will be presented to the PI and study team by the project coordinator during weekly meetings. The review will ensure any repetitive or single, but significant deviations be escalated to the IRB for assessment of whether a non-compliance /deviation may be a potential Serious Breach and determine any necessary response.

15 ETHICAL AND REGULATORY CONSIDERATIONS

15.1 Participant Confidentiality

To track participant outcomes across time while maintaining confidentiality, ID numbers will be used. A separate linking file will be maintained linking the IDs to the respondents' names. The surveys will be conducted using the mobile REDCap database, a password protected, firewalled database only accessible to the research team. Data will be collected using RedCap app. In case of computer problems, we will have paper copies of surveys available. All paper documentation will be maintained in locked files at UNC.

15.2 Expenses and Benefits

Participants will receive \$195 in compensation for participation in data collection and intervention session attendance: \$5 eligibility screening, \$25 for baseline data collection, \$15 for 6 month data collection, \$20 for 12 month data collection, and \$20 for 18 month data collection. Throughout the intervention, participants will receive a \$15 cash incentive for attendance at Group Sessions 4, 8, 12, 16, 20, 24, and \$20 at session 26.

16 PUBLICATION POLICY

The study PI is responsible for intellectual content on publications from the dataset collected for this study. Study PI should determine appropriate authorship and acknowledgements for all scientific publications. Institutional and funder policies should be adhered to. NHLBI should be acknowledged in all publications.

17 ARCHIVING

6 months after the main study outcomes paper is published, de-identified dataset will be available per institutional and federal guidelines. Data will be destroyed five years after the study

publications are complete. For electronic data, we will follow accepted techniques to permanently delete files. This will include destruction of linkage files, transcriptions, data files, web-based database files, digital interviews and all other electronic files. All paper files will be shredded at that time.

